Study Protocol

With the approval of the XXXXXX Clinical Research Ethics Committee dated 26.12.2023 (No. 2023-172) and registration on ClinicalTrials.gov (NCT06241794), this study commenced. The study was conducted as a prospective, randomized, and blinded trial in the operating rooms of XXXXXXXXX Hospital between 01.01.2024 and 01.05.2024. A total of 72 patients, aged 18-65, classified as ASA (American Society of Anesthesiologists) physical status I-II, who were scheduled for laparoscopic cholecystectomy by the general surgery clinic, were included in the study after obtaining written and verbal consent. The study was designed and conducted in accordance with the ethical principles set forth in the Declaration of Helsinki.

Patient randomization was performed using an internet-based software program (Research Randomizer, http://www.randomizer.org/). Patients were randomly assigned to two groups based on the type of nerve block performed:

- Group 1 (n=35): Patients who received a modified thoracoabdominal nerve block via a perichondrial approach (M-TAPA)

- Group 2 (n=37): Patients who received a serratus intercostal plane block combined with a rectus sheath block (SIPB + RSB)

Inclusion criteria:

- Scheduled for laparoscopic cholecystectomy due to cholelithiasis
- ASA physical classification I-II
- Age between 18-65 years
- Body mass index (BMI) <35
- Patients who read and accepted the informed consent form

Exclusion criteria:

- Patients unwilling to participate
- ASA physical classification III or higher
- BMI >35
- Patients unable to score pain using the NRS system

- Patients with allergies to the local anesthetic and analgesic drug used
- Pregnant and breastfeeding patients
- Patients under 18 or over 65 years of age
- Patients with uncontrolled anxiety
- Patients with alcohol and drug addiction
- Patients with neuromuscular diseases and peripheral nerve disorders
- Patients with widespread chronic pain
- Patients with hepatic and renal failure
- Patients with contraindications for peripheral block
- Patients undergoing a second procedure along with laparoscopic cholecystectomy
- Patients with a history of abdominal surgery or trauma
- Patients where laparoscopic surgery was converted to open surgery
- Patients with technical issues using patient-controlled analgesia (PCA) devices
- Patients unable to understand or complete the Quality of Recovery-15 (QoR-15) scale

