Following the completion of the block procedures, neuromuscular blockade was reversed with 4 mg/kg sugammadex (Brimadex, Polifarma ilaç, Tekirdağ) under 80% O2 ventilation. Patients with adequate spontaneous respiration were extubated and transferred to the recovery room. Patients' vital signs, pain scores, and postoperative nausea and vomiting (PONV) scale were monitored in the recovery room. Pain assessment using the numerical rating scale (NRS) was performed at rest (static) and during active movement (transitioning from lying to sitting - dynamic). Pain intensity was rated from 0 (no pain) to 10 (worst imaginable pain). For postoperative analgesia, iv tramadol PCA was administered. The PCA protocol was set to 10 mg bolus tramadol on demand with a 20-minute lockout period without basal infusion. Tramadol consumption was recorded at 0-1 hour, 0-12 hours, 12-24 hours, and the total at 24 hours. Patients with a pain score above 4 in the recovery room received 25 mcg iv fentanyl as rescue analgesia, which was recorded.

Patients with an Aldrete score of 9 or higher were transferred to the ward. Postoperative pain follow-up was conducted by an anesthetist blinded to the group assignment. NRS scores were recorded at 0, 1, 3, 6, 12, 18, and 24 hours postoperatively. All patients received 1 g iv paracetamol every 8 hours for postoperative analgesia. Patients with pain scores above 4 despite the analgesic regimen received 50 mg iv dexketoprofen (Ketavel, Deva İlaç, Kocaeli) as rescue analgesia.

To determine the sensory block's dermatomal level, pinprick testing was performed at 2 and 24 hours postoperatively using a sterile needle along a vertical line 3-5 cm away from the midline and mid-axillary line between the T3-L1 sensory levels. A three-point numerical scale (0 = no prick sensation, 1 = reduced prick sensation, 2 = normal prick sensation) was used. Scores of 0 or 1 were considered effective. Normal sensation in the shoulder was used for comparison.

Patients were monitored for PONV within the first 24 hours postoperatively using a scale (PONV 1: no nausea or vomiting, PONV 2: nausea but no vomiting, PONV 3: single episode of vomiting or persistent nausea, PONV 4: two or more episodes of vomiting or severe/persistent retching). Patients with a PONV score of 2 or higher received 4 mg iv ondansetron. The total ondansetron dose administered within the first 24 hours postoperatively was recorded.

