Patients completed the QoR-15 (Quality of Recovery-15) questionnaire, a self-report measure of postoperative recovery quality, twice: once in the waiting area on the morning of surgery and again 24 hours postoperatively. The time to first oral intake, time to first flatus/stool, and time to first mobilization (standing unaided) within the first 24 hours postoperatively were recorded.

Statistical Methods

The statistical analyses of the data obtained in this thesis were performed using the SPSS software package (Version 22.0, SPSS Inc., Chicago, IL, USA - Licensed by Hitit University). Descriptive statistics were presented as mean \pm standard deviation for continuous data showing normal distribution, median (min-max) for continuous data not showing normal distribution, and number and percentage (%) for categorical data. The normality of the data distribution was analyzed using Shapiro-Wilk tests. To compare the means of two independent samples of continuous variables, the independent samples t-test was used for normally distributed data, and the Mann-Whitney U test was used for data not normally distributed. For comparisons of two dependent groups of continuous variables, the paired t-test was applied for normally distributed data. The Friedman test was used for comparing numerical variables among more than two dependent groups with data not normally distributed. After variance analysis, Bonferronicorrected post-hoc tests were applied to determine the source of differences among groups. Relationships between categorical variables for two independent groups were evaluated using the Chi-square test or Fisher exact test, depending on the cell counts in cross-tabulations. Statistical significance was set at p<0.05.

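### No rule covers patients without a recovery event by 24 h; if there are any and the arms differ, comparing recorded times alone usually understates the difference

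*Combined protocol and SAP*

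**What the plan says.** The last paragraph before Statistical Methods introduces three recovery times: first oral intake, then "time to first flatus/stool, and time to first mobilization (standing unaided) within the first 24 hours postoperatively were recorded". The natural reading applies the 24 h window to all three. It can also be read as applying to mobilization alone.

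For comparing two independent groups on a continuous variable, Statistical Methods gives one pair of tests: "the independent samples t-test was used for normally distributed data, and the Mann-Whitney U test was used for data not normally distributed". The matching summary for skewed data is "median (min-max) for continuous data not showing normal distribution". Chi-square and Fisher tests are listed for categorical data but are not assigned to whether an event had occurred by 24 h.

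The section has no time-to-event method, no censoring rule and no missing-data rule. It does not say what is entered for a patient whose event had not happened when the window closed. No passage names any of the three times as a primary outcome.

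**The concern.** A time recorded only inside a window has no value for a patient whose event falls outside it. Whether the event happens within 24 h is itself a result of treatment, observed after randomization. A comparison of recorded times is therefore made among patients selected on their outcome. The slowest patients are removed, and the slower arm usually loses more of them. That pulls the arms together and discards the evidence that one arm recovers later.

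The descriptive statistics are affected in the same way. A median and maximum taken over recorded times describe only patients who had the event, and the maximum cannot exceed 24 h however slow the others were. Without a count of non-events, a reader cannot tell whether a reported recovery time describes everyone analysed or only those who recovered within the window.

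**Working it through.** The plan gives no figure to reproduce: no expected recovery times, no spread, no non-event rate and no sample-size calculation. The check therefore illustrates the mechanism on assumed inputs.

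**Inputs from the documents.** Arms of 35 (M-TAPA) and 37 (SIPB + RSB); cut-off 24 h; significance level 0.05. Sidedness is not stated, and two-sided is assumed.

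**Assumed inputs.** Lognormal times with log-SD s = 0.5 in both arms, and a median ratio of 4/3 in every row, so that the rows differ only in how close the events lie to 24 h.

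**Step 1: share without the event.** For median m, P(T > 24) = 1 − Φ(ln(24/m)/s).
- m = 8: ln(3)/0.5 = 2.197, giving 1.4%; 35 × 0.014 = 0.5 patients.
- m = 10.7: ln(2.25)/0.5 = 1.622, giving 5.2%; 37 × 0.052 = 1.9 patients.
- m = 12: ln(2)/0.5 = 1.386, giving 8.3%; 35 × 0.083 = 2.9 patients.
- m = 16: ln(1.5)/0.5 = 0.811, giving 20.9%; 37 × 0.209 = 7.7 patients.

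**Step 2: median among recorded times.** With p the share from step 1, this is m × exp(s × Φ⁻¹(0.5 × (1 − p))).
- 12 vs 16 h: 12 × exp(0.5 × −0.104) = 11.4 h and 16 × exp(0.5 × −0.265) = 14.0 h. The recorded-only difference is 2.6 h, against 4.0 h for all patients.
- 8 vs 10.7 h: 7.9 and 10.3 h, a difference of 2.4 h against 2.7 h.
- 4 vs 5.3 h: no visible change, 1.3 h both ways.

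**Step 3: power of the Mann-Whitney test.** This was simulated with 20,000 trials per row, using the normal approximation with tie and continuity corrections. Non-events were either dropped or given one tied worst rank. Repeat runs differ by about 0.01 to 0.02.

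| Medians (h) | Non-events | Dropped | Ranked last | Loss |
|---|---|---|---|---|
| 4 vs 5.3 | about 0% vs 0.1% | 0.65 | 0.65 | about 0 |
| 6 vs 8 | 0.3% vs 1.4% | 0.63 | 0.65 | about 2 points |
| 8 vs 10.7 | 1% vs 5% | 0.59 | 0.66 | about 7 points |
| 10 vs 13.3 | 4% vs 12% | 0.50 | 0.65 | about 15 points |
| 12 vs 16 | 8% vs 21% | 0.42 | 0.64 | about 22 points |

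**Step 4: no true difference.** In five scenarios with identical distributions in both arms, the rejection rate was 0.048 to 0.050 with non-events dropped and 0.047 to 0.050 with them ranked last. The test does not produce excess false positives in that case.

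**Step 5: other shapes.** Thirty further scenarios (exponential, Weibull, lognormal and normal times; assumed median pairs from 6/10 to 16/24 h) gave the same direction. The recorded-only mean difference never exceeded the all-patient difference restricted to 24 h, and power with non-events dropped was never higher than with them ranked last. The direction can fail if the share who never have the event is set separately from timing. With 20% never-events in both arms and medians of 8 vs 11 h, the recorded-only difference was 3.10 h against 2.52 h. Nothing in the documents points to that situation, but it is why the claim says 'usually'.

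**The case against.** The strongest reply is that nothing in the documents triggers the harm. It needs patients without the event by 24 h, their exclusion, and a true difference between the arms, and no passage shows any of these. Entering such patients as later than 24 h and running the listed Mann-Whitney test would also be compatible with the text. If events came early, the loss is 0 to 2 points, as the 4 vs 5.3 h and 6 vs 8 h rows show. The window may cover mobilization only, and the times are not primary.

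Most of this stands, and it limits the weight of the point. The gap itself remains: the plan supplies no value for a non-event, and the sentence on recording supplies none either. The listed Chi-square or Fisher test could compare event status at 24 h, but it is not assigned to these outcomes and would not repair the comparison of times.

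A reader might go further and infer that patients were in fact dropped, that the recovery-time results are therefore biased, or that a significant result would be a false positive. The documents do not support the first two, because they report neither non-events nor how any were handled. The third does not follow either: with identical distributions the error rate stays near 5%.

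**Conclusion.** The point holds as a conditional one. For any recovery time recorded only to 24 h, the plan as written restricts the comparison to patients who had the event. If non-events exist and the arms differ, the difference is usually understated and power is lost. Under the assumed lognormal model at a median ratio of 1.33, the loss runs from nothing when events are early to about 22 points when 8% and 21% of patients lack the event. The actual size is unknown, because every distributional input is assumed. If nobody lacked the event, nothing changes. If the window covers mobilization only, the point applies to that time alone. With no passage naming these times as primary, this is a change to consider, with low to moderate weight.

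**What to change.** For each time recorded only to 24 h, report the number per arm without the event by 24 h and say how they were entered. Where there are any:

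- Keep every analysed patient in the comparison and give non-events a single tied worst rank (>24 h) in the Mann-Whitney test already listed. 'Analysed' is deliberate, since the exclusion criteria allow removal after randomization ("Patients where laparoscopic surgery was converted to open surgery").
- Do not use means or the t-test for that time.
- Show a median or maximum that falls among non-events as '>24 h'.
- Use Kaplan-Meier with a log-rank test, censored at 24 h, only as a sensitivity analysis. Naming one main method avoids a choice made after the data are known.

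If a time has no non-events, say so; the listed tests then stand.

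The cost is a reporting line and a re-run in SPSS, with no new measurements. The trial is described as already completed ("The study was conducted as a prospective, randomized, and blinded trial"), so existing records must be checked to separate 'not yet' from 'not recorded'. Patients were seen at 24 h for pain ("NRS scores were recorded at 0, 1, 3, 6, 12, 18, and 24 hours postoperatively"), for pinprick testing and for the QoR-15, but whether event status was noted then is not stated. If it cannot be recovered, report the missing times per arm and show the comparison both with them dropped and with them ranked last.

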All necessary information regarding the procedures was provided to the randomized patients, and their written consent was obtained. Patients' ASA status and demographic characteristics (gender, age, height, weight, BMI, chronic diseases) were recorded. Surgeons and postoperative follow-up healthcare workers were not informed of the group assignments, maintaining blinding in the study. Preoperative QoR-15 questionnaires were completed before patients were taken to the operating room. Standard anesthesia monitoring (non-invasive arterial blood pressure measurement, heart rate, electrocardiography, peripheral oxygen saturation measurement) was applied to all patients. A 20G catheter was used to establish a peripheral venous line. The induction of anesthesia was recorded. For premedication, 0.03 mg/kg iv midazolam (Sedozolam, Monemfarma, Istanbul) was administered, and after preoxygenation, anesthesia was induced with 2 mg/kg propofol (Propofol-PF, Polifarma, Tekirdağ) and 1 mcg/kg fentanyl (Fentanyl-PF, Polifarma, Tekirdağ). After administering 0.6 mg/kg iv rocuronium bromide (Jecron, Tüm Ekip İlaç, Istanbul) and achieving muscle relaxation, endotracheal intubation was performed. Mechanical ventilation was provided in pressure

controlled mode targeting an end-tidal CO2 value of 35-40 mmHg. Anesthesia was maintained with an O2/air mixture (FiO2: 0.40), sevoflurane (Sevorane, AbbVie, Italy) (minimum alveolar concentration 0.8-1), and iv remifentanil (Ultan, Centurion Pharma, Ankara) infusion. The remifentanil infusion was adjusted in the range of 0.01-0.2 mcg/kg/min to keep the patient's mean arterial blood pressure within 20% of the baseline value. The start time of surgery was recorded. In all laparoscopic cholecystectomy operations, standard 4 trocar sites (umbilicus, epigastric region below the xiphoid, and subcostal area within the right midclavicular and right anterior axillary lines) were used. The operation was performed with the patient in the supine position and 30° reverse Trendelenburg position. Pneumoperitoneum was maintained with CO2 insufflation at an intraperitoneal pressure of 12 mmHg. The patient's intraoperative vital signs were monitored according to routine anesthesia protocol.

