Thirty minutes before the end of the surgery, all patients received 1 g iv paracetamol (Partemol, Vem ilaç, Tekirdağ), 1 mg/kg tramadol (Tramosel, Haver farma ilaç, Turkey), and 4 mg ondansetron (Laufran, Haver pharma, Tekirdağ). After the completion of the surgery, all block procedures were performed under sterile conditions while the patient was supine under anesthesia. The end time of surgery, end time of anesthesia, time of block performance, and duration from block performance to the end of anesthesia were recorded. All blocks were performed under aseptic conditions.

For the M-TAPA block, USG (Logiq V2, GE, USA) guidance was used to identify the transversus abdominis, internal oblique, and external oblique muscles at the level of the 10th rib in the sagittal plane at the costochondral angle with a linear probe. The probe was angled deeply at the costochondral angle adjacent to the 10th rib to visualize the costal cartilage's inferior surface at the midline. Using an in-plane technique, a 22-G, 80-100 mm block needle (B Braun Stimuplex Ultra, 22 G, 80 mm, Germany) was advanced cranially, directing the needle tip towards the posterior surface of the 10th costal cartilage below the chondrium. Twenty milliliters of 0.25% bupivacaine (Buvasin, VEM ilaç, Turkey, prepared by diluting 10 mL 0.5% with 10 mL saline) was injected under the chondrium. The same procedure was performed on the opposite side.

For SIPB, USG guidance identified the serratus anterior and intercostal muscles at the 8th rib level along the right mid-axillary line. A 22-G, 80 mm block needle was used to inject 20 mL of 0.25% bupivacaine between these muscles. SIPB was performed only on the right side.

For RSB, USG guidance placed a linear probe transversely just above the umbilicus and slightly lateral to the midline. After visualizing the rectus abdominis muscle, posterior rectus sheath, and the hypo-echoic space between them, a 22-G, 80 mm block needle was advanced in-plane through the subcutaneous tissue until the needle tip reached the space between the rectus abdominis muscle's epimysium and the posterior rectus sheath. After negative aspiration, 10 mL of 0.25% bupivacaine was injected. Adequate spread was confirmed by lifting the epimysium of the rectus abdominis muscle while depressing the posterior fascia and peritoneum. The same procedure was performed on the opposite side.

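### QoR-15 is measured before the block and at 24 h, but no listed between-arm analysis uses the preoperative score; the plain comparison is valid but, as a t-test, less precise once the correlation exceeds about 0.12

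*Combined protocol and SAP*

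**What the plan says.** The Study Protocol has the QoR-15 completed twice: "once in the waiting area on the morning of surgery and again 24 hours postoperatively". The account of preoperative procedures agrees: "Preoperative QoR-15 questionnaires were completed before patients were taken to the operating room". The blocks come later: "After the completion of the surgery, all block procedures were performed under sterile conditions". The first score therefore cannot have been affected by the block.

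Statistical Methods is a general list of tests. For two independent groups it says "To compare the means of two independent samples of continuous variables, the independent samples t-test was used for normally distributed data", with Mann-Whitney U where normality fails. For two related measurements it says "For comparisons of two dependent groups of continuous variables, the paired t-test was applied for normally distributed data". The rest of the list is the Friedman test with Bonferroni post-hoc tests, and chi-square or Fisher tests. It contains no regression, ANCOVA or other covariate-adjusted model. The reference to variance analysis only introduces the post-hoc tests and names no covariate.

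No sentence assigns a test to QoR-15 or says whether the 24 h score or the change from baseline is compared between arms. The documents name no primary outcome and give no QoR-15 standard deviation or correlation.

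**The concern.** A baseline measurement of the outcome itself is usually the most useful covariate available in a small trial. Here it is collected on every patient, yet no listed between-arm analysis uses it. With 72 patients precision is scarce, and adjustment needs no further data.

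Two less satisfactory uses of the baseline remain open because no test is assigned:

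- **Change scores.** A between-arm t-test on the change from baseline is compatible with the list. With equal SDs it is less precise than ignoring the baseline whenever r is below 0.5.
- **Within-arm paired tests.** The paired t-test needs a continuous outcome measured twice. The other assessment made exactly twice is sensory testing ("pinprick testing was performed at 2 and 24 hours postoperatively"), but that uses a three-point scale. QoR-15 is thus the most likely use, though this is an inference. A before/after test inside each arm does not compare the blocks. If the change were significant in one arm only, a reader could easily take that as a difference between them.

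**Working it through.** **Inputs from the documents.** Arms of 35 and 37, so N = 72 (Study Protocol, opening section); significance at p<0.05 (Statistical Methods). There is no power or precision figure to reproduce.

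**Assumptions.** Two-sided testing (sidedness is not stated); a difference of 0.5 SD for illustration; r between baseline and 24 h score varied from 0 to 0.7; a linear relation with a common slope; roughly normal scores; equal SDs at the two times for the change score.

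**Unadjusted t-test on the 24 h score.** SE = √(1/35 + 1/37) = 0.236 SD. With 70 df the critical value is 1.994, so the half-width is 1.994 × 0.2358 = 0.470 SD. Noncentral-t power at 0.5 SD is 0.552.

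**ANCOVA.** Expected variance relative to unadjusted is (1 − r²) × (N − 3)/(N − 4) = (1 − r²) × 69/68, with 69 df. The factor 69/68 is the cost of estimating the slope.

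**Change score.** Variance relative to unadjusted is 2(1 − r), with 70 df.

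| Assumed r | ANCOVA variance ratio | ANCOVA half-width (SD) | ANCOVA power | Change-score half-width (SD) | Change-score power |
|---|---|---|---|---|---|
| 0 | 1.015 | 0.474 | 0.546 | 0.665 | 0.316 |
| 0.1 | 1.005 | 0.471 | 0.550 | 0.631 | 0.344 |
| 0.2 | 0.974 | 0.464 | 0.563 | 0.595 | 0.380 |
| 0.3 | 0.923 | 0.452 | 0.586 | 0.556 | 0.424 |
| 0.5 | 0.761 | 0.410 | 0.669 | 0.470 | 0.552 |
| 0.7 | 0.518 | 0.338 | 0.828 | 0.364 | 0.770 |

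The unadjusted comparators are 0.470 SD and 0.552 in every row.

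**Break-even.** Setting (1 − r²) × 69/68 = 1 gives r = √(1/69) = 0.120, or 0.122 once the lost degree of freedom is counted. With fewer complete pairs it moves little: √(1/61) = 0.128 at N = 64 and √(1/57) = 0.132 at N = 60.

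**Equivalent sample size.** Dividing 72 by the variance ratio, ANCOVA on 72 patients has the precision of an unadjusted analysis of 72/0.923 = 78 patients at r = 0.3, and 72/0.761 = about 95 at r = 0.5.

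**Simulation checks.** With 100,000 trials per value of r, the variance ratios were 1.015, 0.973, 0.922 and 0.761 at r = 0, 0.2, 0.3 and 0.5. The unadjusted t-test's type I error stayed between 0.049 and 0.051, which confirms that it is valid. A separate simulation of ANCOVA power (40,000 trials per r) agreed with the table to within 0.003.

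**Within-arm paired tests when the blocks are identical.** Let a and b be the power of the paired t-test at n = 35 and n = 37. The chance that exactly one arm is significant is a(1 − b) + b(1 − a). It depends on the assumed common change, in units of the SD of the change:

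| Assumed change | Exactly one arm significant |
|---|---|
| 0 | 10% (2 × 0.05 × 0.95 = 9.5%) |
| 0.2 | 34% |
| 0.33 | 50% (maximum) |
| 0.5 | 28% |
| 0.6 | 12% |
| 0.8 | 0.7% |
| 1.0 | 0.01% |

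**The case against.** The strongest reply is that this is a preference about efficiency. The unadjusted test is valid, no passage contradicts another, and the size of the gain rests on a correlation the documents do not report. At r = 0.2 the half-width falls only from 0.470 to 0.464 SD and power rises by about 1 point; at r = 0.3 the gain is about 3 points. The break-even of 0.12 marks where adjustment stops costing anything, not where it becomes worthwhile. All of this stands and limits the weight of the point.

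It is also fair that the break-even and power figures apply to the t-test. The plan switches to Mann-Whitney U if normality is rejected, and no comparison with that test was calculated.

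The within-arm argument is conditional: the paired test must be used on QoR-15, run separately by arm, reported with p-values and then misread. The plan lists separate between-arm tests and nowhere says that a within-arm result will be used to compare blocks. The risk ranges from 50% to practically nil and disappears if both arms change substantially. Nor does the plan propose a change-score analysis; it only leaves one possible. These parts are cautions about reporting.

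Finally, the documents describe the study in the past tense, so a change now may only be possible as a supplementary analysis.

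None of this removes the core point. A pre-intervention score is held, no listed between-arm analysis uses it, and using it costs at most 0.6 points of power in the setting calculated.

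**Conclusion.** The concern holds as a loss of precision; there is no bias. Compared with the unadjusted t-test on 24 h QoR-15, ANCOVA is more precise for any r above about 0.12 in absolute value. For a 0.5 SD difference the power gain is about 1 point at r = 0.2, 3 points at 0.3, 12 points at 0.5 and 28 points at 0.7, against a loss of 0.6 points at r = 0. These figures rest on assumed correlations, a linear relation with a common slope, roughly normal scores and all 72 patients having both scores.

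The missing covariate model is plain from the text. Which test was meant for QoR-15, and that the paired t-test was meant for it, are inferences. With no primary outcome named, the effect shown is confined to the QoR-15 result. The change should be made, but the trial's validity does not depend on it.

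**What to change.** Replace the general rule for this outcome with a specific sentence in Statistical Methods: 24 h QoR-15 total is analysed by linear regression on assigned arm with preoperative QoR-15 total as covariate, and the adjusted mean difference is reported with its 95% CI. If residuals are clearly skewed, use rank ANCOVA or a bootstrap CI.

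Present before and after values within each arm descriptively, and do not use within-arm p-values as evidence about the blocks.

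The Study Protocol describes patients as already randomised by the time the preoperative form was completed, so also state whether they knew their arm at that point. This bears on how cleanly the score serves as a baseline.

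The cost is one changed sentence, one degree of freedom and under 1 point of power if the correlation is near zero. No new data are needed, and SPSS fits the model. The study period given (01.01.2024 to 01.05.2024) is described in the past tense. If unblinded results have already been seen, label the adjusted analysis post hoc and report the unadjusted test beside it.

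### The plan names no test for the four-level ordered PONV score, and its categorical rule, read literally, gives an unordered test that ignores severity order

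*Combined protocol and SAP*

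**What the plan says.** The postoperative follow-up part of the Study Protocol defines the scale: "PONV 1: no nausea or vomiting, PONV 2: nausea but no vomiting, PONV 3: single episode of vomiting or persistent nausea". The fourth level is repeated vomiting or severe retching. The levels are therefore ordered by severity. The score is followed over the first 24 hours. The only cut-point the protocol uses is a treatment trigger: "Patients with a PONV score of 2 or higher received 4 mg iv ondansetron".

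Statistical Methods assigns tests by type of variable, not by outcome. For two independent groups there are two routes:

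- The first opens "To compare the means of two independent samples of continuous variables". It gives the t-test for normal data and adds that "the Mann-Whitney U test was used for data not normally distributed".
- The second reads "Relationships between categorical variables for two independent groups were evaluated using the Chi-square test or Fisher exact test", with the choice between the two depending on cell counts.

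The section defines no ordinal class, names no trend test, and does not mention PONV. It also does not say whether PONV is analysed on four levels, as yes/no, or as a number.

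**The concern.** A score made of four labelled grades fits the categorical route more naturally than the continuous one. On that reading PONV is tested by chi-square or Fisher on a 2x4 table. Neither test uses the order of the columns: shuffling the four labels leaves the p-value unchanged. The test spreads its sensitivity over three degrees of freedom, most of which concern patterns other than more or less nausea and vomiting.

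In a trial of 72 patients, a real shift in PONV severity is then more likely to be reported as no difference. The test itself also yields no summary of how large the shift is. And because the text leaves more than one reading open, the PONV test could be chosen after the results are known.

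**Working it through.** **Inputs from the documents.** Arms of 35 and 37 (Study Protocol, group list), four ordered PONV levels, and "Statistical significance was set at p<0.05". Sidedness is not stated; two-sided is assumed. The documents contain no power calculation, PONV rate or effect size, so there is no stated figure to reproduce.

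**Assumptions.** Six reference distributions over PONV 1/2/3/4, from 25/25/25/25% to 80/12/5/3%, and a common odds ratio (OR) of 2 to 5 towards less PONV in the other arm. Each cumulative probability c becomes c' = OR·c / (1 − c + OR·c). For 50/25/15/10 and OR 2.5, the cumulative values 0.50, 0.75, 0.90 become 0.714, 0.882, 0.957. The other arm is then 71.4/16.8/7.5/4.3%.

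**Tests compared.**
- Pearson chi-square on the 2x4 table, with degrees of freedom equal to the non-empty levels minus 1.
- Fisher-Freeman-Halton exact test.
- Mann-Whitney with z = (W − n1(N+1)/2)/√V, where V = (n1·n2/12)·[(N+1) − Σ(t³ − t)/(N(N−1))] and t is the number of patients at each level.

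There were 40,000 simulated trials per scenario (1,000 for the exact test).

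| Reference distribution, OR | Chi-square | Exact | Mann-Whitney | Loss, chi-square | Loss, exact |
|---|---|---|---|---|---|
| 50/25/15/10, OR 2 | 0.201 | 0.197 | 0.318 | 37% | 38% |
| 50/25/15/10, OR 2.5 | 0.328 | 0.325 | 0.490 | 33% | 34% |
| 40/30/20/10, OR 3 | 0.485 | 0.514 | 0.671 | 28% | 23% |
| 40/30/20/10, OR 5 | 0.809 | 0.820 | 0.922 | 12% | 11% |
| 80/12/5/3, OR 2 | 0.082 | 0.129 | 0.175 | 53% | 26% |
| 80/12/5/3, OR 3 | 0.165 | 0.236 | 0.334 | 51% | 29% |
| 25/25/25/25, OR 5 | 0.871 | 0.863 | 0.953 | 9% | 9% |

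Loss is 1 − (power of the unordered test / power of Mann-Whitney). Over the whole grid it runs from 9% to 53% for chi-square and from 9% to 38% for the exact test. With no true difference, Mann-Whitney rejects in about 5% of trials. Chi-square rejects in 3-4% at the most skewed distributions, so part of its loss there is conservatism.

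**Direction of the shift.** Moving the second arm towards more PONV gives smaller losses at large effects. With 40/30/20/10, 50/25/15/10, 60/20/12/8 and 70/15/10/5, the chi-square loss is 30-35% at OR 2.5 and 14-18% at OR 4.

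**Analytic check.** Suppose all the signal lies in the ordered direction. A 1-df test with power P has noncentrality λ = (1.960 + z_P)², and the 3-df test has the same λ.

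| Rank-test power | 0.30 | 0.50 | 0.70 | 0.80 | 0.90 |
|---|---|---|---|---|---|
| 3-df power | 0.20 | 0.35 | 0.53 | 0.65 | 0.78 |
| Loss | 34% | 31% | 24% | 19% | 13% |

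For 80% power the 3-df test needs λ = 10.90 against 7.85, and 10.90/7.85 = 1.39 times the patients. Put the other way, 72 patients then do the work of 72/1.39 ≈ 52.

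**Which unordered test would apply.** The plan gives no cell-count threshold. Under the usual criterion of expected counts of at least 5, every level needs t × 35/72 ≥ 5, so t ≥ 10.3, or at least 11 of the 72 patients. With shifts towards less PONV, 92-100% of tables from the five skewed distributions fail this, and the exact test would mostly be used.

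**Where the ranking of the tests changes.** For 50/25/15/10 against 50/48/1/1, chi-square has power 0.79 and Mann-Whitney 0.15. With a yes/no split at PONV 2 or higher, power is close to the rank test when at least 60% score 1 (60/20/15/5, OR 3: 0.56 against 0.55).

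**The case against.** The strongest reply is that the plan never sends PONV to chi-square or Fisher. A reader might infer that it does, but the text supports this only as the most natural literal reading. Two others are possible. One is a yes/no analysis at the score that triggers ondansetron. The other is Mann-Whitney on a number from 1 to 4. Statistical Methods uses continuous and numerical loosely, and the 0-10 pain score is also discrete and also unnamed there. This stands, and it limits the finding to what the rule yields if applied to all four levels. It does not remove the need to name the test: if several readings are open, the choice can follow the data.

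A reader might also infer a fixed loss of about a third. The documents cannot support one figure, because they give no PONV rates or effect size.

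Third, the rank test is not always better. Routine ondansetron before the end of surgery, and again at score 2, could hold down the upper grades and produce a difference that is not a uniform shift. This stands as a real cost of the change. It does not outweigh the gain against a shift in severity, which is what a graded scale is built to detect.

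Finally, counts and percentages are planned for categorical data, so direction would be visible in the tables. That is correct; what is missing is a test and an estimate that use it.

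**Conclusion.** The point holds in limited form. The PONV scale is ordered, Statistical Methods names no test for it, and the literal categorical rule applied to all four levels gives an unordered test. Under assumed proportional-odds shifts with 35 against 37 patients, that costs roughly 10-50% of the rank test's power with chi-square and roughly 10-40% with the exact test. About a third is a fair description only where rank-test power is around 0.3 to 0.5, and even there very skewed distributions depart from it.

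The consequence is contained. The documents do not designate PONV as the primary outcome, and at OR 2 to 2.5 the rank test itself has power of only about 0.18 to 0.56 over the distributions tried. The change improves the comparison without making it well powered. Nothing here shows that a PONV result from this trial is wrong.

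**What to change.** Add to Statistical Methods:

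- The ordered PONV score is compared between groups by the Mann-Whitney U test with tie correction, or by a proportional-odds model reporting a common odds ratio with 95% CI. The model has the advantage of giving an effect size.
- The per-patient score analysed over 0-24 h is stated, for example the worst one.
- Chi-square and Fisher are kept for binary and unordered variables.
- Counts and percentages at each PONV level are reported by group, so that a non-monotone difference can be seen.

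The cost is a few lines of text, using a scale already recorded and, for the first option, a test the plan already names. The statistical price is lower, possibly much lower, power against non-monotone differences. The Study Protocol describes the trial as already conducted between January and May 2024. If the test is named after the PONV data have been seen, the report should say so and show the originally implied analysis alongside.
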